**[[contact]](mailto:[contact])**

**5/30/2014**

**Revised**

**7/16/2014**

## **INTRODUCTION/BACKGROUND MATERIAL/PRELIMINARY STUDIES AND SIGNIFICANCE**

Despite the new growth of SMS interventions and early promising studies in other areas, there have been no published SMS studies with problem drinkers looking to change their drinking, and to our knowledge there have been no SMS studies across any health problem or disorder that has directly compared tailored vs. untailored messaging and the effects of dynamically timed-interactive messaging vs. statically timed messaging outcomes. As a recent NIH review of mobile health interventions highlights, we need to test new behavior change models with the advent of mobile technologies and incorporate the adaptive capabilities into our treatments (Riley, Rivera et al., 2011). Our previous work on the feasibility of using text messages with disenfranchised individuals in addiction treatment revealed that 98% are interested in using SMS to help them stay drug free and that individuals preferred different types of messaging at different periods of recovery.

According to the National Institute on Alcohol Abuse and Alcoholism, problem or risky drinking is defined as greater than 7 standard drinks per week for women and 14 standard drinks per week for men. Other groups have other criteria (e.g. 10 drinks for women and 14 for men per week). The Institute of Medicine reports that problem drinkers are those with mild-to-moderate problem severity who do not have physical dependence. These individuals are not severe enough to meet criteria for tolerance and withdrawal but still report trouble controlling their drinking. These individuals are not likely to seek treatment but are interested in methods to reduce their drinking.

The large literature from other areas reveals that SMS interventions offer several unique benefits that appear generalizable to warranting their examination with individuals in PD. First, messaging interventions inherit the benefits of internet interventions (e.g. low cost, standardized, individualized, adaptable and tailored, allow for data collection) but there is no need for an internet connection, or to use a computer following the initial assessment (or ever). Second, unlike mobile apps, SMS interventions do not require a smart phone, custom software programming for specific phones, application updates, and are accessible on most phones making the intervention significantly more accessible and generalizable than smart phone apps. Third, SMS ready phones can perform nearly all the functions of standalone ecological momentary assessment (EMA) devices without additional hardware or custom programming. There is an emerging literature on the using of text messaging to capture EMA data and results reveal similar outcomes to PDAs and IVR (Berkman, Dickenson, et al., 2011). One great advantage of SMS is it does not require the person to be immediately present like interactive voice response EMA.

The study entitled, Tailored Mobile Text Messaging to Reduce Problem Drinking (PD) is designed to develop and test a tailored adaptive text messaging/short message service (SMS) intervention for individuals interested in reducing their alcohol consumption.

Tailored interventions are individualized to the persons need states to make it more relevant and persuasive. Excessive alcohol consumption is a serious personal and public health issue and economic problem to society. Despite the significant consequences of problem drinking (PD), most persons with alcohol problems never seek formal treatment. While the emergence of internet based interventions (IBIs) has expanded access and brief intervention opportunities to PDs, they suffer from high attrition, limited ability to proactively meet individuals where PD occurs and adapt to real-time needs (e.g. high craving). Recent evidence from smoking cessation studies highlight that SMS interventions may provide the needed reinforcement to help individuals enhance self-regulation and reduce problem alcohol use. Moreover, there is evidence that since problem drinking has regular episodic patterns for which tailored interactive designs may be particularly effective.

## **OBJECTIVE(S)/SPECIFIC AIMS AND HYPOTHESES**

This study is now in the recruitment phase. We are comparing different types of messaging in 240 PDs over a 12-week period. We are comparing 5 types of messaging: 1) tailored content and timed messaging adaptive to the participants current state (Beta Intervention); 2) Tailored content messaging (not adaptive or timed) sent at 6pm every day; 3) untailored consequence based messages sent at 6pm every day; 4) untailored benefit based messaging sent at 6pm every day and 5) Brief feedback and EMA only. In addition, we have a “goal only” group that does not mention alcohol. Web-based assessments will be completed at screening, baseline, at week 4, week 12 and through weekly EMA via SMS.

This is an exploratory study to generate effect sizes for a larger R01 trial. Our exploratory aims are as follows. Primary Aim: To test whether the Tailored-adaptive treatment arm is superior to EMA only and the content tailored only arm and the consequence and benefit messaging arms to EMA only in reducing weekly drinking/drinks per drinking day and percent days heavy drinking over the course of the 12 week intervention. Hypothesis 2a: Tailored-adaptive arm will be superior to the content tailored only and consequence and benefit messaging study arms in reducing weekly drinking/drinks per drinking day and heavy drinking days. Hypothesis 2b: Tailored-only messaging will be superior to consequence and benefit messaging arms in reducing weekly drinking/drinks per drinking day and heavy drinking days. Hypothesis 2c: All supportive messaging arms will be superior to assessment only in reducing weekly drinking/drinks per drinking day.

## **EXPERIMENTAL DESIGN**

Overview: Participants are recruited through online recruitment on both social networking sites and alcohol screening sites. If a participant is interested they complete a brief survey online and if they are eligible they are instructed to call the researcher at a time that fits their schedule. The research assistant will review the

eligibility criteria and go over the consent form on the phone. Participants complete a 10 question quiz about the protocol in the form of a consent form quiz to ensure comprehension. They are also trained on filling out the weekly assessment text messages. Once enrolled and randomized, they receive messaging for 12 weeks and complete assessments at baseline, week 4 and week 12 as well as weekly EMA. Once individuals complete the study they will be given a \$40 gift card to amazon. They are compensated \$15 for the baseline survey, \$5 for the week 4 survey, and \$15 for the week 12 survey. Primary outcomes include drinks per drinking day, days heavy drinking, and average drinks per week as measured through week EMA. Additional outcomes will include drinking related consequences, goal commitment and intervention satisfaction.

This study is now in the recruitment phase. We have already developed all messaging groups and done preliminary research on user preferences with 50 problem drinkers and 400 individuals on messaging preferences. This IRB protocol is only for the actual testing of the different forms of messaging in 240 individuals. The primary intervention group is the adaptive tailored group which includes messages tailored to a baseline survey results (including drinking times) and adaptive to ongoing drinking patterns and goal achievement via interactive ecological momentary assessment (EMA) which is real-time assessment and responses that are tailored to the persons current functioning. Other features include participant initiated help messaging and support network (e.g. spouse) alerts. We are testing the intervention with 240 PDs over a 12-week period. We are comparing 5 types of messaging: 1) tailored content and timed messaging adaptive to the participants current state (Beta Intervention); 2) Tailored content messaging (not adaptive or timed) sent at 6pm every day; 3) untailored consequence based messages sent at 6pm every day; 4) untailored benefit based messaging sent at 6pm every day and 5) Brief feedback and EMA only. In addition, we have a "goal only" group that does not mention alcohol. Web-based assessments will be completed at screening, baseline, at week 4, week 12 and through weekly EMA via SMS. All individuals are offered an additional 12 weeks of messaging in the group of their choice.

Description of Procedures:

**Please note: This study is done completely over the web and phone. There are no office visits at all. It is all distant virtual interaction.**

A brief bullet point review of general procedures is below:

- Recruit problem drinkers online
- Screen potential participants online
- Create phone screening appointment
- Offer consent form for review prior to call
- Screen participant on the telephone
- Obtain consent on the phone (participant completes after eligibility and it will be reviewed by staff prior to enrollment).

- Explain procedures (12 week study)
- Guide individual to complete baseline assessment
- Randomize participant
- Sign each individual participant up for the messaging program
- Review how to respond to assessment messages.
- Review procedures based on group assignment (What to Expect)
- Provide contact information of the RA & PI
- Email participants at week 4 to ensure safety and concerns (Week 4 Survey)
- Contact at week 12 for assessment (Week 12 Assessment)
- Offer referrals
- Offer additional 12 weeks of messaging without assessments.

Screening: Interested parties can learn about study recruitment through a number of web resources, including AlcoholScreening.org, Moderation Management, etc. Prospective participants will click on the ad to be sent to our secure web form, where they will be welcomed and given a brief description of the study aims and a warning not to complete the screening if intoxicated or in need of emergency care. If they choose to continue, they will be directed to generate a unique participant ID. They will be instructed to record this ID in a secure location, and proceed to the preliminary Screening Survey in Survey Monkey. If ineligible, they will be directed to a Survey Monkey page containing an extensive list of online resources and referrals. If eligible, they will be directed back into the Project AAIMS webform, where they will be required to provide their first name, initials, email and phone number. After doing so, they will be directed to a scheduling platform, where they can select a timeslot for an initial phone screening, to be completed with a member of the AAIMS staff. Upon selecting and confirming the appointment, they and the staff will be sent an email with the time and date of the phone appointment, and a reminder to read the Consent Form and complete the attached Consent Form Quiz prior to the call. The responsible AAIMS staff member will then call the prospective participant at the appointed time to go through the phone screening and determine eligibility. All forms with actual data are stored on the Survey Monkey server only with one's code. All other information is stored on a secure server with no questionnaire data.

Baseline Assessment: To complete the baseline assessment individuals login to survey monkey and enter their unique code to identify them. IP address is not collected. This will occur once the participant has confirmed their information with the research assistant who will provide them with the study website and code while they are on the phone. No codes will be given over email. The reason for this is to ensure participant information is confidential and secure. Once enrolled, participants will complete the baseline battery of measures described in the assessments section via the web-based assessment in their secure portal.

Similar to our current studies, the RAs will assess potential participants and when a question or concern is present, flag the case to have the clinician review the data and speak directly with the potential participant. RAs are trained to have a low threshold to speak with the clinician on duty and a clinician is available at all times during both

screening and follow-up appointments. We already had a double review of the first 20 clients where the RA and a trained therapist each independently spoke with the potential participant and there

**Randomization:** Once participants complete the baseline assessment they will receive the brief feedback on safe drinking levels and be automatically randomized into one of the five treatment arms stratified by gender, alcohol consumption, and readiness for change. The split for stratification is as follows: Gender: Male and Female; Severity: Above 24 drinks for men and above 21 drinks for women; Readiness score: 0-7 (low); 8-10 (high). Based on these scores separate envelopes are created (envelope randomization method), where the RA chooses an envelope and places the participant in one of the 5 study conditions randomly chosen. We stratify to ensure proper heterogeneity across groups. Each grouping has an equal number of study conditions to ensure any one group (e.g. male, high severity, high effort) is represented across groups. At the half-way point of the study, we will examine how well balanced each of the groups are with regard to the stratification variables and weight the conditions in the envelopes accordingly.

Individuals who drop out after randomization will not be replaced and we will conduct intent to treat analysis on all individuals who receive at least 1 day of text messages. While the research assistant will review the study arms with the participants in general during consent, individuals randomized to the different study arms will be given individualized instructions on what to expect. During the course of the intervention all participants will be allowed to call the RA for any reason and will be able to pause their messaging for 24 hour periods.

**Follow-up Assessment:** We will conduct a brief web-based week 4 assessment to assess drinking variables and overall functioning. This is 15-20 questions. Three days before their 12-week completion date participants will be sent a reminder text and email to complete the final assessment via a web-based survey. The week 12 assessment will include all the baseline measures as well as an item on perceived relevance of the intervention content to them specifically (Strecher, Shiffman, & West, 2006), treatment history during the intervention, overall recommendations to improve the intervention in addition to additional resources for PD. During the course of the study, additional data elements such as the number of eligible vs. ineligible participants, reasons for exclusion, referral sites, length of time to complete the screening and each assessment, and numbers of persons who drop out at any point in the study and at which point they drop out.

**Ecological Assessment:** Once the study begins all subjects will receive weekly ecological assessment for assessment only purposes (TA arm will also receive interactive assessment). **Weekly Drinking:** Three items will be sent every seven days including: The number of drinking days in the last week, the average number of drinks per drinking day in the last week, and number of drinking days where more than 5 drinks were consumed (4 for women) in the last week. We will also ask about

improvement over the course of the week to both assess change but also guide the adaptive intervention group. We chose this time to send messages during the day to reduce the chances that individuals will be intoxicated while reporting their drinking in their natural environment. Shiffman (2009) highlights the use of EMA to collect data from drinking and substance abusing populations and highlights while some have shown mild intervention effects (e.g. Collins et al., 1998) that most show little reactivity. Moreover, collecting weekly drinking assessments should reduce the likelihood of reactivity.

#### Study Treatments:

All SMS arms will first be given brief feedback on safe drinking levels in addition to messaging. This is specifically designed to test whether the addition of messaging enhances feedback on safe drinking but also ensure that all participants have access to a credible intervention. We will make every effort to reduce the chances that participants will be unblinded to their study condition – particularly individuals in the EMA condition. During the consent process we will inform participants that we are comparing different types of frequencies of text messaging including assessing drinking patterns and commitment through text messaging to see how it affects drinking.

**Tailored Adaptive (TA):** The TA treatment will be developed during the first phase of the study and tested in the RCT against the other study treatment arms. The intervention includes tailored messaging content and timing and frequency parameters initially based on a web-based assessment but adaptive based on current goal attainment and commitment. See Figure 1 in Human Subjects for a diagram of the intervention features. The messaging in the tailored adaptive will both be tailored to the baseline assessment results as well as to the participants current functioning. For example, a client low in confidence to change at baseline will receive messages to boost confidence. However, unlike in the TO condition, messages in the TA condition will change over the course of the study based on the participants current level of functioning. For example, if a participant responds to an SMS assessment message that they have a craving, they would receive craving messages (e.g. A craving does not mean you have to drink, it only means you have a craving) or if their confidence has increased that would NOT receive messages to boost their confidence in general.

**Tailored Content Only (TO):** The TO treatment arm will include tailored messaging based on the baseline assessment only sent at 6pm daily. Numerous IBIs and SMS studies have used baseline assessment information to tailor content throughout the intervention. Tailored content interventions are perceived as more relevant than untailored interventions. To our knowledge, this is the first study to compare a tailored adaptive over time intervention with multiple contacts to a baseline only limited contact tailored intervention. The messaging in the TO condition will be tailored to the baseline assessment results only. For example, a client low in confidence to change at baseline will receive messages to boost confidence throughout the study (e.g. Once you start to believe you can change, you can start the process of changing).

**Consequence Messaging (CM):** The consequence messaging arm will include messages on the consequences of PD sent at 6pm daily and is based on the previous literature using the Health Belief Model to induce change. Consequence based messaging was the experimental condition in the only messaging study (using PDAs) to date designed to reduce alcohol consumption. Moreover, in our own work we found that individuals who preferred consequence based messaging to benefit driven messaging scored lower on readiness for change which is consistent with the general print tailoring literature. Messages in this condition will highlight the consequences of alcohol use in various life domains (e.g. heavy alcohol use increases the risk of heart conditions OR heavy alcohol use is associated with poor sleep quality).

**Benefit Messaging (CM):** The benefits messages will be similar to the consequence messaging arm but will include messages on the benefits of changing sent at 6pm daily. In our own work we found that individuals who preferred benefit driven messaging scored higher on readiness for change which is consistent with the general print tailoring literature. Messages in this condition will highlight the benefits of decreasing of alcohol use in various life domains (e.g. When you control your drinking you end up waking up refreshed and ready for the day).

**Ecological Momentary Assessment Only (EMA):** The EMA only arm will include the four weekly EMA items (Commitment to change (1x week), drinking days, average drinks per drinking day, number of heavy drinking days). Because intensive EMA can be an intervention within itself due to ongoing self-monitoring EMA across all conditions will be limited to three days and five total messages including three messages about weekly drinking sent on Sunday early afternoon. The EMA condition is designed to test whether brief feedback and weekly monitoring can reduce PD compared to active SMS interventions. The EMA only condition will send individuals assessment messages only (e.g. how committed are you to not drink heavily in the next 24 hours or how many days this week did you drink alcohol).

**No Alcohol Messages (Goal Only):** Messages that are general goal directed messages without the mention of alcohol will be offered to all individuals who are concerned about confidentiality. At present - we have placed 15 people in this group. While we will assess this group compared to other groups, they will be analyzed separately because of forced randomization. The "Goal Only" group was created to protect the safety of participants who were concerned about confidentiality and includes messages that are very general and do not explicitly refer to drinking or alcohol e.g. "Remembering your goals tonight when you go out will help you realize them tomorrow".

**Measures & Schedule of Events (See Attached)**

Measure	Construct	Time					Optional Messaging
		Screen	Intervention Messaging Period			Weeks 12-24	
			Baseline (Randomize)	Weekly EMA	Week 4	Week 12	
Demographics	-	X	X			X	
QFV-30 questionnaire*	Alcohol consumptions last 30 days	X			X		
QFV-90 questionnaire*	Alcohol consumptions last 90 days		X			X	
EMA (Drinking Days, Drinks per Drinking Day, Heavy Drinking Days)	Weekly alcohol consumption			X			X
Frequency of Drug Use	Frequency drug use last 30 days	X				X	
Tx History & Medications	Substance abuse and mental health treatment history (last year) and current medications.	X				X	
Short Alcohol Withdrawal Scale*	Alcohol withdrawal potential	X					
Short Inventory of Problems*	Alcohol related consequences		X			X	
3-Item Primary Appraisal Measure: Alcohol	Subjective harm from use, continued use and benefit to stopping		X		X	X	
The Obsessive-Compulsive Drinking Scale*	Craving, salience and loss of control over alcohol		X			X	
Drinking Norms Rating Form	Perceptions of participants own and others drinking behavior		X			X	
Drinking Goals	Daily and weekly consumption goals	X	X		X	X	
Typical Drinking Patterns	When individuals are most likely to drink heavily		X		X	X	
Goal Commitment	Commitment to moderation and individual goals		X	X	X	X	
Single item rulers	Readiness to change, importance, and confidence to change.		X		X	X	
Triggers Questionnaire	Situations that may trigger heavy drinking		X			X	
Relevance of intervention to needs	Single item on whether material was relevant to participant				X	X	

Other sources of help sought	Outside help sought during the intervention					X	
Satisfaction and recommendations	Overall program satisfaction and recommendations.					X	

\*Validated scales

A brief description of the site(s) where the research is to be conducted, including information about the adequacy of facilities for the safe and appropriate conduct of the research, and relevant demographic and epidemiological information about the country of region concerned.

**INCLUSION AND EXCLUSION CRITERIA**

Inclusion and exclusion criteria will be ascertained via: 1- a web-based screening form and 2- through a phone call with the research assistant.

Participants who respond to the internet advertisements or come directly to the study home page will complete a brief eligibility screener as well as a phone screening which will include QFV-30 questionnaire which assesses drinking patterns (Miller, 1996; 2 minutes) with examples of standard drinks, a face valid frequency of drug use scale within the last month, Short Alcohol Withdrawal Scale (Gossip et al., 2002; SAWS; score of 12 or above), and a brief assessment of mental health treatment and current medications. In addition, all potential participants will be asked about their messaging plan, if they are willing to receive between 15 to 120 text messages per month for the next three months (See Screening and Phone Screening Documents).

Inclusion: Participants must:

- (a) be fluent and able to read in English at the eighth grade level; (Self report and consent form quiz)
- (b) be between the ages of 21 and 65; (self-report; age in demographics)
- (c) have an estimated average weekly consumption of greater than 12 or 15 standard drinks per week for women and men, respectively; (self-report; QFV-30 questionnaire)
- (d) be willing to reduce their drinking to non-hazardous levels ; (Self-report)
- (e) be willing to provide informed consent; and
- (f) own a mobile phone and have an active email address and are willing to receive and respond to up to 120 text messages total per month (average about 50). (self-report in demographics questionnaire)

Exclusion: Participants will be excluded from the study if they:

- (a) present with significant substance use or a current substance use disorder (for any substance other than alcohol, nicotine, or caffeine), which is defined as greater than once weekly use in the past month; (Frequency of Drug Use Questionnaire). Marijuana can be used up to 2x a week.

(b) present with a serious psychiatric illness or suicide risk as measured by previous inpatient treatment, medications for psychosis or recent suicidality; (Treatment history form & self-report; a current self-reported or clinician determined diagnosis of Major Depression or past or present bipolar disorder, delusional disorder or schizophrenia (self-report and clinical interview).

(c) demonstrate clinically severe alcoholism, as evidenced by physical withdrawal symptoms or a history of serious withdrawal symptoms (e.g., hallucinations, seizures, or delirium tremens), and score greater than 12 on the Short Alcohol Withdrawal Scale (SAWS).

(d) report a medical condition that precludes drinking any alcohol – including pregnancy (self-report) or

(e) Unable to understand research study procedures as evidenced a score of less than 7 out of 10 on the consent form quiz (consent form quiz).

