Participants will be recruited through the internet and before any messages are sent will be contacted by a research assistant to review the consent form – including an explanation of the study protocol, its risks, potential benefits, and alternative treatment. Additionally, all participants must complete the consent form quiz to ensure comprehension. An entire copy of the informed consent form will be available for download by the participant. Protection against risk - Inclusion criteria and the use of trained research staff following the initial screening will minimize acceptance of participants with severe alcohol use disorders into the study. Participants with a history or current symptoms of alcohol withdrawal will be referred to more intensive care. During the intervention phase, participants' alcohol use will be monitored through EMA. If a participant reports drinking at greater level, the RA will call the participant. Participants will be given the emergency numbers of the PI and study RA for consultation. Participants who have dropped out of study treatment and are interested in returning to the program or attending another program will be referred for appropriate treatment according to their needs and wishes. We will not be asking individuals sensitive information about harm to self until we have contact information so we can contact them. Numerous studies have been conducted over the internet and mobile phones without any subject contact. There have been more internet based intervention studies for alcohol use than any other disorder. We have significantly

more information that most studies in that we will have actual contact with the individuals in the study by telephone prior to the study beginning then again at week 4 and week 12. Regular SMS reminders will be sent to individuals enrolled in all arms of the study to remind them 1) if they want standard treatment, they can call the RA and be helped with referrals and 2) if they are worsening clinically, they can call for help. If a participant is threatening to harm themselves or another we will use standard protocol to inform the proper authorities as if it was a patient through phone contact as we will have their address and phone number. This will be determined based on email, phone, mobile or web-based data from the participant. We have had no adverse events with the first 104 individuals enrolled.

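### Read literally, exclusion (c) requires a SAWS score above 12 even when there is a history of withdrawal seizures or delirium tremens, contrary to the protocol's own risk section

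*Protocol*

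**What the plan says.** Protocol, Inclusion and Exclusion Criteria, exclusion (c), removes people with severe alcoholism. The evidence it names is current physical withdrawal symptoms or else "a history of serious withdrawal symptoms (e.g., hallucinations, seizures, or delirium tremens), and score greater than 12 on the Short Alcohol Withdrawal Scale".

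The paragraph on screening instruments in the same section gives the scale with a different threshold, "SAWS; score of 12 or above". It does not say what that score triggers.

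Discomforts and Risks says that the criteria, together with trained staff, "will minimize acceptance of participants with severe alcohol use disorders into the study". The next sentence reads: "Participants with a history or current symptoms of alcohol withdrawal will be referred to more intensive care". It contains no SAWS condition.

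Experimental Design adds a safeguard at screening: "RAs are trained to have a low threshold to speak with the clinician on duty".

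**The concern.** Exclusion (c) itself treats past withdrawal hallucinations, seizures or delirium tremens as signs of severe alcoholism. It then appears to require a high SAWS score as well. Someone with such a history who has no withdrawal symptoms when screened could score low, and research staff who apply the sentence as written would not exclude that person.

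What is at stake is safety at entry. Participants must "be willing to reduce their drinking to non-hazardous levels", and they do so remotely: "There are no office visits at all". Later monitoring looks mainly for increased drinking, so it is not aimed at a participant who runs into trouble while cutting down. Screening is therefore the main protection for a person with past serious withdrawal. None of the planned analyses is affected.

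**Working it through.** No sample size or power figure is involved. The check compares the rule under each reading of the sentence with the risk section.

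**Inputs**

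- S = current physical withdrawal symptoms (exclusion (c))
- H = history of serious withdrawal (exclusion (c))
- W = SAWS above 12 (exclusion (c))
- Risk section: refer if S or H, with no W. Its wording covers any withdrawal history, so it includes H.

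**Readings of exclusion (c)**

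- A: (S or H) and W. The score conditions everything before it.
- B: S or (H and W). The score conditions only the history.
- L: S or H or W. This is a loose list of separate indicators.

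| S | H | W | A | B | L | Risk section |
|---|---|---|---|---|---|---|
| 0 | 0 | 0 | in | in | in | no referral |
| 0 | 0 | 1 | in | in | out | not addressed |
| 0 | 1 | 0 | **in** | **in** | out | refer |
| 0 | 1 | 1 | out | out | out | refer |
| 1 | 0 | 0 | in | out | out | refer |
| 1 | 0 | 1 | out | out | out | refer |
| 1 | 1 | 0 | in | out | out | refer |
| 1 | 1 | 1 | out | out | out | refer |

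(in = not excluded by (c); out = excluded.)

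**Results**

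1. Serious history, no current symptoms, SAWS 12 or less (third row): not excluded under A or B, the two readings that keep the word and. The risk section refers this person, so the texts conflict.
2. Current symptoms with SAWS 12 or less (fifth and seventh rows): excluded under B but not under A. This case is only ambiguous.
3. Under L the gap in result 1 closes, but L requires reading and as or.

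**Other criteria.** Exclusion (a) concerns other substances, (b) psychiatric illness and suicide risk, (d) medical conditions that rule out drinking, including pregnancy, and (e) the consent quiz. None names withdrawal. Exclusion (d) might catch some of these people indirectly.

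**Cut-off.** The sets SAWS ≥ 12 and SAWS > 12 differ at one value, exactly 12.

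**The case against.** The strongest reply is that the sentence is a loosely punctuated list. There is a comma before the word and, and the lead-in can be carried forward to mean people who show severe alcoholism and also people who score above 12. The risk section, which treats history or symptoms as enough, supports this as the intent. This largely stands as a statement of intent. It does not rescue the wording: nothing in (c) says that any one item suffices, and the literal reading is the conjunctive one.

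A second reply is that the risk section and clinician review already cover the case. They are real safeguards. However, the risk section speaks of referral and does not list an exclusion, although its place beside the sentence on keeping severe cases out makes non-enrolment the natural meaning. Clinician review depends on someone seeing a concern, and literal use of (c) raises none.

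A reader might go further and infer that withdrawal history is never asked about. In the schedule of measures, the SAWS is the only withdrawal measure among the six marked at screening, and the treatment item is described as "Substance abuse and mental health treatment history (last year) and current medications". The documents do not support that inference. The screening forms are not shown, and the same table also omits pregnancy, suicidality, the messaging plan and the consent quiz, all of which are ascertained. The missing row shows nothing about what the forms ask.

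The cut-off mismatch is also fairly called minor. It concerns one score, and one of the two statements is a parenthesis with no stated consequence.

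**Conclusion.** The point holds as a wording defect that bears on safety. Taken literally, exclusion (c) does not exclude a person with past withdrawal hallucinations, seizures or delirium tremens who has no current symptoms and a SAWS of 12 or less. That conflicts with the risk section. The conclusion rests on giving the word and its ordinary meaning and on taking referral to more intensive care to mean non-enrolment.

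The number of people affected is not given and cannot be derived. A reader might infer that such people have been enrolled; the documents do not show this. The protocol reports no adverse events among the first 104 enrolled, and the screeners may already apply a stricter rule. Nor can it be said that people with current symptoms and a low score are missed, since that depends on how the sentence is grouped. The conflict over a score of exactly 12 is a minor addition.

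**What to change.** Reword exclusion (c) so that severe alcoholism is shown by any one of three things:

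- physical withdrawal symptoms; or
- a history of serious withdrawal, keeping the present examples; or
- a SAWS score of 12 or above.

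Use 12 or above in both the screening paragraph and the criterion; it is the stricter of the two values now written. Leave the sentence on referral in Discomforts and Risks as it is, because it is the clearer and wider safeguard. Confirm that the web and phone screeners ask about past serious withdrawal and apply the reworded rule.

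The cost is one reworded criterion and a check of the screener logic. There is one substantive change to declare: a SAWS of 12 or above becomes excluding on its own, which the literal text does not now require (second row of the table, and a score of exactly 12). Somewhat fewer people will be eligible; the protocol gives no figure from which to estimate how many.
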